#### 7.9.1. Discontinuation of trial treatment

If a randomised participant decides that they no longer wish to continue receiving trial treatment they should continue their trial follow up visits in accordance with the protocol unless they also request to be withdrawn from this aspect of the trial.

If the participant commenced their allocated trial drug and subsequently chooses to withdraw from trial treatment (or is withdrawn due to loss of mental capacity), it is recommended that the participant completes the weaning period off their medication (see dose schedules in section 8.6). Depending on the dose the participant is receiving at the time of the discontinuation, they may require a slower weaning period; this is at the discretion of the PI or delegated medically trained doctor.

If a participant chooses to withdraw from both trial treatment and follow up visits, passive data collection of safety data and additional therapies for FHP from medical records will be collected where possible unless the participant explicitly requests their medical records are not accessed.

The participant should not be unblinded unless it is considered medically necessary for the participant's safety by a medically qualified doctor.

#### 7.10. Collection and storage of CT scans and blood samples

As part of the trial, participants can provide optional consent for collection of blood samples and for copies of their CT performed as standard of care to be used for future research.

#### 7.10.1. Collection, transfer and storage of CT scans

Participants are not required to have any additional CT specifically for the trial; however, participants will be asked if their CT scan(s) performed as standard of care can be collected and stored for future research. This will include the CT scan reviewed at their MDT to confirm a diagnosis of FHP, and any additional CT scan(s) performed during the participants' routine follow up for FHP during their participation in the trial.

If a participant agrees to this optional component of the trial (as indicated on the informed consent form), the CT scan(s) will be pseudonymised by the local site with participant ID number and sent to a third-party vendor (Qureight Ltd). Qureight Ltd are a UK based company that routinely receive and store NHS patient CT scans through their secure online portal. CT scans from consenting participants will be uploaded by the local site to the Qureight portal. Details of how to complete this process will be provided in a 'Submitting CT scans for future research' work instruction. The CT scans will be stored securely by Qureight in compliance with UK GDPR. Qureight is registered with the NHS Data Security and Protection toolkit.

### 7.10.2. Blood samples for future research

If a participant provides consent to collect bloods samples for future research, these will be collected at the baseline visit and the week 12 follow up visit. The whole blood will be obtained and shipped ambient via post (in a Royal Mail Safe Box) to the Exeter NIHR Clinical Research Facility at Royal Devon University Healthcare NHS Foundation Trust (a Human Tissue Authority licenced laboratory). Details of this process will be provided in a 'Blood for future research' work instruction. Once the samples have been received at the Exeter Clinical Research Facility, they will be processed and stored at -80°C as serum, plasma and whole blood. Any remaining blood samples that were stored for future research will be destroyed after 15 years.

#### 7.11. End of trial

The end of the trial is defined as when the last participant has completed their week 35 end of study telephone follow up, all data queries have been resolved, the trial database has been locked and pre-specified analyses are complete. A declaration of end of trial form will be submitted to the MHRA and NHS REC that awarded the favourable opinion within 90 days of the end of trial.

If the trial is terminated early, the trial will end on the date the Sponsor formally declares the trial terminated in writing. The MHRA and NHS REC will be notified of early termination within 15 days of the Sponsor deciding to end the trial.

#### 8. TRIAL TREATMENTS

Participants will be randomised to receive either 26 weeks prednisolone or 26 weeks placebo on a 1:1 ratio.

#### 8.1. Name and description of investigational medicinal product(s)

Prednisolone is the IMP in this trial with a matched placebo. Prednisolone is the standard corticosteroid used for lung conditions in the UK (except for COVID-19 pneumonia). In the

CHORUS trial, the tablet oral form of prednisolone is being used in both 5mg and 1mg doses, which are over-encapsuled. There will be a matched placebo oral capsule.

#### 8.2. Regulatory status of the drug

Prednisolone has marketing authorisation in the United Kingdom.

The IMP is being processed for this trial (for blinding purposes) in the following ways: deblistering and over-encapsulation with backfill, before repackaging into secure tamperproof containers, with blinded labels as per MHRA annex 13 labelling requirements. IPS Pharma will be contracted to complete these activities. The capsules are HPMC green/green size 00 capsules containing Hydroxypropylmethylcellulose, water, Dye – copper complex of chlorophyllins E141ii. The placebo capsule will be backfilled with an excipient of prednisolone. Full details can be found in the Investigational Medicinal Product Dossier (IMPD).

### 8.3. Product Characteristics

For details of product characteristics, please refer to the provided Summary of Product Characteristics (SmPC).

#### 8.4. Drug storage and supply

Full details can be found in the pharmacy manual. The prednisolone and placebo will be provided directly to sites by the contracted IMP supplier. It will be delivered to sites in batches with the first delivery prior to site greenlighting to open to recruitment. Deliveries will be receipted by the pharmacy department at sites and recorded as received on a trial specific IMP management database. If stock of the trial drug (and placebo) packs is required to be stored away from the local site pharmacy for any reason, please contact ExeCTU for approval.

A drug accountability record will be maintained and updated by delegated site staff for all IMP packs provided and dispensed. The delegated persons at the sites will keep records of the receipt, dispensing, returns, quarantine or destruction of trial medication. The blinded pack IDs will be used to identify the packs on the accountability logs. A file note should be included in the Pharmacy Site File (PSF) directing to the location of these records. At the end of the trial, the drug accountability record should not be destroyed without Sponsor authorisation. All data regarding the trial medication must be recorded either on forms provided by ExeCTU or on local accountability forms authorised by ExeCTU.

#### 8.5. Preparation and labelling of Investigational Medicinal Product

Preparation and labelling of the IMP will be completed by the contracted IMP supplier IPS pharma in accordance with annex 13 of Good Manufacturing Practice (GMP) guidelines. Full details can be found in the pharmacy manual.

For blinding purposes, the active drug will be over-encapsulated. Placebo capsules will be manufactured to match in appearance but will not contain any active ingredients.

Active and placebo capsules will be packaged both strengths will be packed into High Density Polyethylene (HPDE) containers with a poly propylene child resistant cap (120 capsules per container for the 5mg dose and 100 capsules per container for the 1mg dose) with tamper-evident seals. All containers will be labelled with unique pack IDs.

#### 8.6. Dosage schedules

The IMP packs to be prescribed and dispensed to the participant upon randomisation will be allocated by the randomisation system within the main trial database (REDCap) by the research team.

For subsequent dispensing visits, and the allocation of single additional packs, site research staff must log directly into the IMP management system (IMP-MS) to allocate the packs. For further details please see pharmacy manual.

The Randomisation system or IMP-MS will automatically return the correct quantity of pack IDs of the correct type and dose (1mg or 5mg prednisolone or 1mg or 5mg placebo) for the specific visit. Confirmation of the pack IDs will be emailed to the site team (PI, research nurses/coordinators and pharmacy team).

At their baseline visits participant will be provided with a trial treatment diary with guidance of how to take their trial treatment and their planned daily dose schedule.

#### 8.6.1. Intervention period

#### Prednisolone 5mg or matched placebo

For the intervention period (weeks 0 to 25) participants will be provided with over-encapsuled prednisolone/ matched placebo in 5mg (or equivalent) capsules. Prednisolone 5mg or matched placebo will be prescribed and dispensed at baseline (at randomisation) and the inperson week 12 follow up visit.

An initial peak dose of 40mg (8 capsules) per day will be given for two weeks, followed by dose reduction of 10mg until reaching a maintenance dose of 10mg (2 capsules) per day by week 12 post-randomisation (i.e. 40mg/day (8 capsules) for 2 weeks, then 30mg/day (6 capsules) for 4 weeks, then 20mg/day (4 capsules) for 4 weeks, then 10mg/day (2 capsules) maintenance). The maintenance dose of 10mg/day (2 capsules) will be continued for the remainder of trial intervention period (i.e. to 26 weeks post-randomisation). See Table 3 and Figure 3 for details.

Treatment Day	Total daily dose (if on active treatment)	Prednisolone 5mg/placebo Capsule(s)/day	Prednisolone 1mg/placebo Capsule(s)/day	Number of weeks taken
		Dispensing visit	- Baseline	
0-13	40mg	8	0	2
14-41	30mg	6	0	4
42-69	20mg	4	0	4
70-83	10mg	2	0	2
		Dispensing visit	- Week 12	
84-181	10mg	2	0	14
	L	Dispensing visit	- Week 26	
182-188	5mg	1	0	1
189-202	4mg	0	4	2
203-216	3mg	0	3	2
217-230	2mg	0	2	2
231-245	1mg	0	1	2
		Week 35 End o	of study	

All participants will be provided with additional prednisolone 5mg/matched placebo to act as a "buffer" for trial compliance, medically approved dose escalations and late follow-up visits. See Dose modification section 8.7

#### 8.6.2. Weaning period

#### Prednisolone 1mg or matched placebo

For the weaning period (week 26 to 34) participants will be provided with over-encapsuled prednisolone/ matched placebo in 1mg (or equivalent) capsules. The weaning schedule is summarised in Table 3 and Figure 3. Prednisolone 1mg or matched placebo will be prescribed and dispensed at the end of treatment week 26 in person visit.

#### Figure 3: Dose schedule, visits and weaning period

The planned dose schedule for the intervention and weaning periods along with the scheduled participant contact visits are documented in Figure 3. The weaning period (week 26 to 34) was designed to mitigate against the risk of possible adrenal suppression. The weaning algorithm shown in Figure 4 was produced in collaboration with endocrinology colleagues [name], [name], [name] from Royal Devon University Healthcare Foundation Trust.

Figure 4: IMP weaning algorithm

#### 8.7. Dosage modifications

This trial has been designed to mimic clinical practice wherever possible and it is anticipated that investigators may want to increase the IMP for short periods of time based on clinical events, such as 1. Intercurrent infections/exacerbations or 2. perceived respiratory deteriorations (symptomatically) on dose titration from 40mg to 10mg. Or investigators may want to dose reduce from 40mg to 10mg at faster rate than outlined in section 8.6.1 for example if the participant experiences significant psychiatric events believed to be related to higher doses of prednisolone.

Participants have been provided with additional IMP to allow a short-term increase in IMP to occur in a blinded fashion. While the final decision on dosage will be left to discretion of the treating local investigators, we would recommend the following:

- 1. For intercurrent infections/exacerbations: a standard escalation to 6 capsules (30mg) for 7 days, with reduction thereafter back to previous dose of IMP
- 2. For perceived deteriorations in symptoms during the titration period (Days 0 to 70) then the local investigator may increase the IMP to the last previously effective dose for 7 days, then reattempt a further wean down to the planned dosing schedule.

If the dose modifications are not successful then the local investigator should contact the trials team to discuss the appropriate next steps.

#### 8.8. Known drug reactions and interaction with other therapies

A full list of known adverse effects of prednisolone is detailed in the Summary of Product Characteristics (SmPC). Please see the risk section 2.1 for more information of the key safety risks.

#### 8.9. Concomitant medication

All concomitant medications including over the counter medications should be reported on the concomitant medications eCRF in REDCap.

#### 8.9.1. Non-permitted concomitant medication

Participants are not permitted to take any the following medication whilst in the CHORUS trial:

- Hepatic microsomal enzyme inducers/ Antiepileptics: phenytoin, rifabutin, carbamazepine
- Hepatic microsomal enzyme inhibitors/ antifungals: ketoconazole
- Antibacterials: Rifamycin

If a participant has taken or is currently any of the non-permitted concomitant medications, please contact the CHORUS trial manager via [contact] for further advice.

A full list of prednisolone interactions can be found in the prednisolone SmPC.

#### 8.9.2. Additional immunosuppressive therapies

After the week 12 follow up visit, additional immunosuppressive therapies can be prescribed at the discretion of the investigating site, which can include second line mycophenolate and azathioprine and the addition of anti-fibrotics, nintedanib. Any additional immunosuppressive therapies should be reported on the additional therapies eCRF in REDCap.

#### 8.9.3. Supportive medication

Investigating sites should assume that the participants are on prednisolone and can prescribe any supportive medication supplied as usual standard of care. Any supported medications should be reported on the concomitant medications eCRF in REDCap.

#### 8.10. Trial restrictions

Participants of childbearing potential are required to use highly effective contraception for the duration of their participation in the trial (35 weeks from randomisation), as defined in the eligibility criteria section 6. Breastfeeding mothers and pregnant people are not eligible to participate in this trial.

#### 8.11. Assessment of compliance with treatment

Every randomised participant will be provided with a participant trial treatment diary. This will be used to help the participant to log their daily trial treatment and record any side effects they may have experienced.

This participant trial treatment diary can be used by the participant during their follow up visits to inform the research team of any adverse events, missed doses or dose modifications that have occurred since the last visit, or to confirm the trial treatment has been taken as planned. Please note these diaries can be reviewed by the research team however they will not need to be transcribed in REDCap.

During their follow up visits participants will be ask to self-report their IMP compliance by answering the following question;

Since your last follow-up visit, which of the following options best describes

how often you took your trial treatment?

- Never
- Less than half the time
- About half the time
- More than half the time
- Nearly all the time
- All the time

This will be recorded on the visit follow up eCRFs. If the participant has been advised by their clinical team at the hospital to modify their trial treatment dose (see section 8.7) this should be recorded on the IMP Dose modification eCRF in REDCap. For guidance on how to report adverse events or serious adverse events reported at the follow up visits please see pharmacovigilance section 9.

Participant will be advised to return all unused IMP during their follow up visits for safe disposal, all IMP can then be destroyed in accordance with local pharmacy practice.

The local trial pharmacy teams will be responsible for maintaining and updating the drug accountability log in the CHORUS Pharmacy Site File (PSF) or ISF as per the CHORUS pharmacy manual.

#### 9. PHARMACOVIGILANCE

#### 9.1. Definitions

#### Table 4: Adverse event definitions

Term	Definition
Adverse Event (AE)	Any untoward medical occurrence in a participant to whom a medicinal product has been administered, including occurrences which are not necessarily caused by or related to that product.
Adverse Reaction (AR)	An untoward and unintended response in a participant to an investigational medicinal product which is related to any dose administered to that participant.
	The phrase "response to an investigational medicinal product" means that a causal relationship between a trial medication and an AE is at least a reasonable possibility, i.e. the relationship cannot be ruled out.
	All cases judged by either the reporting medically qualified professional or the Sponsor as having a reasonable suspected causal relationship to the trial medication qualify as adverse reactions. It is important to note that this is entirely separate to the known side effects listed in the SmPC. It is specifically a temporal relationship between taking the drug, the half-life, and

	the time of the event or any valid alternative aetiology that would explain the event.		
Serious Adverse Event (SAE)	A serious adverse event is any untoward medical occurrence that:		
	
 
results in death
 
is life-threatening
 
requires inpatient hospitalisation or prolongation of existing hospitalisation
 
results in persistent or significant disability/incapacity
 
consists of a congenital anomaly or birth defect
 
		
	In addition for this trial		
	
 
acute respiratory exacerbations that require attendance to accident and emergency (A&E) will be reported as an SAE
 
		
	Other 'important medical events' may also be considered serious if they jeopardise the participant or require an intervention to prevent one of the above consequences.		
	NOTE: The term "life-threatening" in the definition of "serious" refers to an event in which the participant was at risk of death at the time of the event; it does not refer to an event which hypothetically might have caused death if it were more severe.		
Serious Adverse Reaction (SAR)	An adverse event that is both serious and, in the opinion of the reporting Investigator, believed with reasonable probability to be due to one of the trial treatments, based on the information provided.		
Suspected Unexpected Serious Adverse Reaction	A serious adverse reaction, the nature and severity of which is not consistent with the information about the medicinal product in question set out in the reference safety information:		
(SUSAR)	
 
in the case of a product with a marketing authorisation, this could be in the summary of product characteristics (SmPC) for that product, so long as it is being used within its licence. If it is being used off label an assessment of the SmPCs suitability will need to be undertaken.
 
in the case of any other investigational medicinal product, in the investigator's brochure (IB) relating to the trial in question
 
		

# Severity classifications

#### Table 5: Adverse event severity classifications

	An event that is easily tolerated by the patient, causing minimal discomfort and not interfering with everyday activities.
	An event that is sufficiently discomforting to interfere with normal everyday activities.
Severe event	An event that prevents normal everyday activities.

#### 9.2. Expected adverse events associated with a trial drug

The reference safety information (RSI) for this trial is section 4.8 of the supplied pharmacovigilance reference copy of the prednisolone SmPC.

#### 9.3. Recording and reporting of Adverse events (AEs)

The safety reporting period will begin from the time of randomisation up to the week 35, End of Study telephone follow-up. The recording and reporting requirements are summarised in the safety reporting flowchart in Figure 5. Adverse events should be reviewed at every follow up visit.

Figure 5: Safety reporting flow chart

All adverse events will be assessed for seriousness and causality as per the definitions in section 9.1 above. These assessments should be carried out by the site PI, or delegated medically qualified doctor, and recorded in the medical notes. If the adverse event is possibly, probably or definitely related to prednisolone it is considered an adverse reaction (AR) and must be reported in the adverse event eCRF in REDCap. In addition to this any viral, fungal or bacterial infections of any kind are considered Adverse Events of Special Interest (AESI) for this trial and must be reported on the adverse event eCRF. If the adverse event doesn't meet the definition of serious and is not considered to be an AESI or AR it should only be documented in the participants medical notes but not be reported on the adverse event eCRF.

All related and unrelated adverse events that are considered serious, as defined in section 9.1, must be reported as an SAE. Additional guidance for reporting serious adverse events can be found in section 9.4 below.

As this is a blinded trial, adverse events should be evaluated on the assumption that the participant was allocated the active drug i.e. prednisolone. The blind should only be broken where knowing the allocation is clearly necessary and will alter the appropriate medical management of the participant. If unblinding is necessary, please refer to the Emergency Unblinding section of the protocol (7.7.1) and the CHORUS 'Unblinding' working instruction.

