## vi. TRIAL SUMMARY

Trial Title	A multi-centre double-blind randomised placebo-controlled group- sequential superiority trial to assess the effectiveness and cost- effectiveness of oral Corticosteroids in patients witH fibrOtic hypeRsensitivity pneUmonitiS							
Short title	CHORUS							
Clinical Phase	Phase 3	Phase 3						
Trial Design	group-sequential, superiority tria	Double-blind, randomised (1:1) placebo-controlled, multi-centre, group-sequential, superiority trial, with internal pilot phase and parallel health economic evaluation.						
Trial Participants		ypersensitivity pneumonitis (FHP) t previously/currently treated for FHP						
Planned Recruitment Target	222							
Treatment Duration	26 weeks + 9 week weaning per	riod						
Follow-up Duration	26 weeks from randomisation							
Planned Trial Period	48 months:							
	M1 to M9 Trial set-up							
	M10 to M34 Participant recrui	tment (including internal pilot phase)						
	M14 to M41 Follow up							
	M42 to M48 Analysis and writ	e-up						
	Objectives	Outcome Measures						
Primary	Assess the effectiveness of 26 weeks of treatment with prednisolone versus (vs) placebo, on disease progression, using force vital capacity (FVC)	Change in absolute forced vital capacity (FVC) (measured using the pulmonary function test) from baseline to 26 weeks post- randomisation						
Secondary								
	Assess effectiveness of prednisolone vs placebo on disease progression at 12 weeks	A i) Change in absolute FVC from baseline to 12 weeks post- randomisation						
	post-randomisation using: A. FVC	A ii) Percentage change in FVC from baseline to 12 weeks post- randomisation						
	A iii) Absolute change in percent predicted FVC from baseline to weeks post-randomisation							
	Assess effectiveness of prednisolone vs placebo on disease progression at 26 weeks	A i) Percentage change in FVC from baseline to 26 weeks post- randomisation						
	A. FVC B. Diffusion Co-efficient for	A ii) Absolute change in percentage predicted FVC from baseline to 26 weeks post-randomisation						
	carbon monoxide (DLco)	B i) Absolute change in DLco (recorded using the European						

		Respiratory Guidelines) from baseline to 26 weeks post-randomisation			
		B ii) Percentage change in DLco from baseline to 26 weeks post- randomisation			
		B iii) Absolute change in percentage predicted $DL_{CO}$ from baseline to 26 weeks post-randomisation			

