	Assess initiation of antifibrotic therapy / additional immunosuppressive therapy	i) Initiation of antifibrotic therapy given by 26 weeks post- randomisation			
	during the 26-week treatment window	ii) Additional immunosuppressive therapy given by 26 weeks post- randomisation window			
	Assess effect of prednisolone vs placebo on participant-reported outcome measures (PROMs) of	Changes from baseline to (i) 12 and (ii) 26 weeks post-randomisation measured using:			
	quality of life, including disease- specific quality of life measures, at baseline, week 12 and week 26	
 
EQ5D-5L Health-Related Quality of Life Questionnaire
 
Living with Pulmonary Fibrosis (L-PF) Questionnaire (dyspnoea, cough and fatigue domain scores of principal interest)
 
Cough Visual Analogue Scales (VAS)
 
Global rating of change (Patient Global Impressions – Severity (PGI-S) scale)
 
			
	Assess safety of prednisolone	Safety data will be collected in accordance with MedDRA. Specific events of interest are:			
		
 
Adverse reactions
 
Respiratory hospitalisations
 
Acute exacerbations
 
Weight gain/ increased waist circumference
 
Adverse events of special interest- infections (see section 9.3)
 
Death
 
			
	Assess health/social care service resource use	Health/social care Resource Use Questionnaire collected at baseline, 12 and 26 weeks post-randomisation			
	Assess cost-effectiveness of prednisolone vs placebo over 26 weeks of treatment	Health economic evaluation via collection of data at baseline, 12 and 26 weeks post-randomisation using the EQ5D-5L and Resource Use Questionnaire			
Investigational Medicinal Product(s)	Prednisolone (and matched place	ebo)			

Formulation, Dose, Route of Administration	Oral prednisolone or matched placebo capsules. Starting at 40mg/day, titrated to 10mg/day maintenance dose by Week 12 and continue 10mg/day until Week 26. Then gradually weaned off by
	week 35 (see trial treatment section 8.0).

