Prolonged administration of prednisolone can result in adrenal suppression and abrupt withdrawal could result in acute adrenal insufficiency. To minimise this risk all randomised participants will follow a weaning schedule at the end of the trial treatment period to slowly reduce their dose before stopping the trial treatment (see section 8.6.1)

Randomised participants will also be given a steroid and clinical trial participation alert card to present to any healthcare professional if they require any type of treatment for the duration of their time on the trial. The alert card will state that the participant may be taking steroids and that they cannot suddenly stop taking them, along with details of how to contact the research team at the hospital who are responsible for the participant and how to access support for emergency unblinding (see blinding section 7.7.1).

If the participant wishes to stop taking the IMP or discontinues the IMP early due to adverse events it is still advised that participants follow a weaning schedule (see section 7.9.1). Participant is made aware of this in the PIS and consent form.

A detailed risk assessment carried out by ExeCTU and reviewed by the Sponsor and TMG will be maintained and updated throughout the trial and will be used to inform the trial monitoring plan.

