#### 7.8. Follow-up assessments

#### 7.8.1. Telephone follow up visits

All participants will be contacted via telephone\* at week 4 and week 8 post-randomisation; this is a safety precaution during the IMP dose reduction phase of the treatment schedule. During these calls, delegated research team should ask the participant if they have experienced any adverse events, if there have been any changes to their concomitant medications and the participant's self-reported IMP compliance (please see trial assessments in section 7 and assessment of compliance in section 8.11).

\*Please note if there any safety concerns the participant can be seen in clinic for these visits.

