#### 7.8.4. End of study telephone follow up visit

All participants will be contacted via telephone\* at week 35 post-randomisation. During this call, a delegated research team member should ask the participant if they have experienced any adverse events, if there have been any changes to the concomitant medications or if they have been prescribed any additional immunosuppressant or antifibrotic medication. The participant will be asked to self-reported IMP compliance during the weaning phase (see section 8.6.2) The participant can return any unused medication to pharmacy at their next standard of care clinic visit for the purpose of safe destruction as per the hospitals local policy.

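### For participants who complete the planned schedule, safety reporting closes at the last planned dose, so events first arising after full cessation are not systematically collected

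*Protocol*

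**What the plan says.** Section 9.3 of the protocol states: "The safety reporting period will begin from the time of randomisation up to the week 35, End of Study telephone follow-up". Other sections use the same limit. Open serious events are followed to outcome or week 35 (9.4.2, 9.9), deaths are notifiable within the safety reporting period (9.4.3), pregnancies are reported to week 35 (9.6), and participation ends there (15.9). Section 7.8.4 places the last contact "at week 35 post-randomisation. During this call, a delegated research team member should ask the participant if they have experienced any adverse events". No visit window is given for that call.

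On treatment, the dose table in 8.6.1 has its last row at days 231 to 245, labelled as two weeks, followed directly by the week 35 end of study. Section 8.6.2 says: "For the weaning period (week 26 to 34) participants will be provided with over-encapsuled prednisolone/ matched placebo in 1mg (or equivalent) capsules". The trial summary's account is "Then gradually weaned off by" week 35.

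On risk, section 2.1 says: "Prolonged administration of prednisolone can result in adrenal suppression and abrupt withdrawal could result in acute adrenal insufficiency". It presents the wean as the means of reducing that risk, and 8.6.2 likewise gives adrenal suppression as the reason for the wean. For participants who stop trial treatment early, 7.9.1 asks them to stay in follow-up and allows that "they may require a slower weaning period; this is at the discretion of the PI or delegated medically trained doctor".

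**The concern.** Assessing the safety of prednisolone is a secondary objective (3.2), and the DMC is to look for patterns in unblinded safety data (9.4.1). The protocol singles out a risk linked to withdrawal, but for anyone who follows the schedule the observation window stops when the drug does. An adrenal event, hospital admission or death in the days or weeks after the last capsule would not be asked about, would fall outside the reporting requirement, and would not reach the DMC or the safety tables. A low count of post-cessation harm could then reflect the window and not the drug.

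Two features add to this. First, the window is anchored to randomisation, so any slippage in the wean shortens off-drug observation or makes it negative. Second, the calls at weeks 4 and 8 are justified because "this is a safety precaution during the IMP dose reduction phase of the treatment schedule", whereas Table 2 schedules no contact between week 26 and week 35, when the dose is taken to zero.

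**Working it through.** **1. Dose table (8.6.1).** The stated durations are 2 + 4 + 4 + 2 + 14 = 26 weeks of treatment, then 1 + 2 + 2 + 2 + 2 = 9 weeks of wean, 35 weeks in all. Week 35 = 35 x 7 = day 245, which reproduces the last day in the table.

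Row length = last day - first day + 1. Every row equals its stated weeks x 7 except the last: 245 - 231 + 1 = 15 days, against 2 x 7 = 14. A 14-day row would end on day 244.

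The text in 8.6 describes the intervention as weeks 0 to 25 and the wean as weeks 26 to 34. If week k covers days 7k to 7k + 6, these are days 0 to 181 (7 x 25 + 6) and days 182 to 244 (7 x 34 + 6). On that numbering the text and the table differ by one day.

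**2. Off-drug observation on the planned schedule.** Day of the week 35 call minus day of last dose:
- last dose on day 245: 245 - 245 = 0 days
- last dose on day 244: 245 - 244 = 1 day

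The step-down from 10 mg to 1 mg (days 182 to 245) lies inside the window, and adverse events over that time are reviewed at the week 35 call.

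**3. Early discontinuers (7.9.1).** Assume, for illustration only, a nine-week wean from stopping week t. Off-drug collection = 35 - (t + 9) weeks:
- t = 12: 14 weeks
- t = 20: 6 weeks
- t = 24: 2 weeks

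It is longer if the wean is shorter or not taken. To be on trial medication still at week 35, a participant stopping at week t would need a wean longer than 35 - t weeks: over 23 weeks for t = 12, over 11 weeks for t = 24.

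**4. Visit window at week 26 (-14/+7 days).** The tabulated wean ends 245 - 182 = 63 days after day 182. If the wean started at the visit itself:
- earliest visit, day 168: last dose on day 168 + 63 = 231, giving 14 off-drug days
- latest visit, day 189: last dose on day 189 + 63 = 252, giving -7 days, so reporting closes with a week of dosing left

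The protocol does not say that the wean starts at the visit. Its first week uses 5 mg capsules dispensed at week 12 (7.8.3). The 1 mg capsules are first needed on day 189 = 182 + 7, the last day of the visit window. A late visit therefore need not delay the wean, and the -7 days is a possibility only.

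**5. Trial summary calendar.** Follow-up is given as 26 weeks from randomisation, and the calendar lists "M14 to M41 Follow up". With 30.44 days per month, 245 / 30.44 = 8.05 months. Recruitment runs through M34, so participants randomised in that month reach week 35 between 33 + 8.05 = 41.05 and 34 + 8.05 = 42.05 months. That is 0.05 to 1.05 months past the end of M41. At 0.4 per site per month and 30 sites, this concerns about 0.4 x 30 = 12 participants.

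**The case against.** The strongest reply is that most of the withdrawal risk is already observed. Section 2.1 ties acute insufficiency to abrupt withdrawal, the wean is there to prevent that, and all nine weeks of it fall inside collection. Between visits, participants have the site's contact details, access to unscheduled visits and a steroid alert card (2.1). Sites must report serious events within 24 hours of awareness (9.4). Serious events still open at the end pass to the GP or clinical team (9.4.2). The week 35 limit is applied consistently across the safety sections, and a call made late would pick up some off-drug days. All of this stands. None of it provides planned observation after full cessation in participants who complete the schedule.

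A reader might infer more than the documents support:
- **That nobody is observed off drug.** Section 7.9.1 keeps early discontinuers in follow-up, and they can contribute weeks of off-drug data.
- **That anyone given a slower wean is still on drug at closure.** That provision concerns participants who discontinue early. It matters only if they stop late or the wean is very long.
- **That a late week 26 visit necessarily pushes dosing past week 35.** The capsule supply does not force this.
- **That the M41 date cuts off safety reporting for late recruits.** It is a planning calendar. Sections 7.8.4 and 7.11 carry every participant to the week 35 call, so this is an inconsistency to tidy and not a loss of data.
- **That the last-dose date is bound to be lost.** Clinician-advised changes go on a dose modification form (8.11) and week 35 collects compliance. However, Table 2 lists dose modification review only at weeks 12 and 26, and the compliance question does not ask for a date.

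**Conclusion.** The point holds in this limited form. On the planned schedule there are 0 days of off-drug safety observation, or 1 day depending on how the last table row is read. Adverse events first arising after full cessation, including adrenal insufficiency, are therefore not systematically collected in participants who complete treatment. Events during the wean, and off-drug events in early discontinuers who remain in follow-up, are collected. Closure while a participant is still taking trial medication is possible if the wean is delayed or prolonged, but the documents give no basis for saying how often.

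This rests on the week 35 call taking place at day 245, since no window is stated for it. The weaning algorithm (Figure 4) and safety flow chart (Figure 5) are not reproduced in the text reviewed, so any provision there could not be checked. The primary FVC analysis is unaffected. What is at stake is how complete the safety objective is, and the remedy is cheap enough to be worth making.

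**What to change.** Define the end of the safety reporting period relative to the last dose of trial medication in 9.3, 9.4.2, 9.4.3, 9.6 and 9.9. The off-drug interval should be chosen by the sponsor and investigators, as the documents give no figure for it. Then either re-time the end-of-study call (7.8.4, Table 2) to that point, or keep it at week 35 and add a later records check for serious adverse events. Record the date of last dose at that contact.

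Reconcile three related places with the end of follow-up finally adopted: the last dose-table row (15 days against a two-week label), the week 26 to 34 description of the wean, and the trial summary's 26-week follow-up and M41 close. Which dosing days are right is for the sponsor and investigators to settle.

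The cost is a protocol amendment, matching participant information, and one re-timed call or one added records check. Last-participant follow-up and database lock move later by the chosen interval, and recall of weaning compliance is slightly longer if the call is moved. No dosing change is involved.
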